1. INTRODUCTION

The purpose of this reporting and analysis plan (RAP) is to describe the analyses to be included in the Clinical Study Report for Protocol:

Revision Chronolog	y:	
2017N332348_01	30-NOV-2017	Original
2017N332348_02	25-JAN-2018	Amendment 1
2017N332348_03	21-MAR-2018	Amendment 2
2017N332348_04	29-MAY-2018	Amendment 3
2017N332348 05	11-DEC-2018	Amendment 4

2. SUMMARY OF KEY PROTOCOL INFORMATION

2.1. Changes to the Protocol Defined Statistical Analysis Plan

The following changes were made from the originally planned statistical analysis specified in protocol GlaxoSmithKline Document Number 2017N332348_05 [(Dated: 11-DEC-2018)]:

Protocol	Reporting & Analysis Plan		
Statistical Analysis Plan	Statistical Analysis Plan	Rationale for Changes	
 Section 10.3: the populations described are Enrolled, Randomised, Evaluable, Safety, PK, PK/PD. 	 Section 4: the populations described are Enrolled, Screened, Safety, PK. 	 Randomised and Evaluable population not needed in any table, figure or listing. PK/PD population and Safety population coincide. Enrolled population needed for Tables of Age Ranges. 	

Due to the early termination of the study, the planned exploratory analysis detailed in the protocol will not be included in the main SAC delivery. Exploratory analysis will be performed separately in cases where it is deemed clinically or scientifically relevant. The study was terminated prior to any subjects being dosed with study treatment in Part B and therefore only minimal listings of screening data will be produced for this part.

207546

2.2. Study Objectives and Endpoints

Objectives	Endpoints
Primary	
• [P1] To evaluate the safety and tolerability of single and repeat oral doses of GSK3358699 in healthy male participants.	 AE reporting. Laboratory safety data (clinical chemistry, haematology, urinalysis). Vital signs (blood pressure, heart rate, body temperature). 12 lead ECGs.
Secondary	
• [S1] To evaluate the systemic pharmacokinetic (PK) profile following single and repeat oral doses of GSK3358699 in healthy male participants.	 Plasma concentrations of GSK3358699 plus derived PK parameters.
• [S2] To evaluate the systemic PK profile of the acid metabolite, GSK3206944 following single and repeat oral doses of GSK3358699 in healthy male participants.	 Plasma concentrations of GSK3206944 plus derived PK parameters.
• [S3] To evaluate the intracellular PK profile of GSK3206944 in target cells following single and repeat oral doses of GSK3358699 in healthy male participants.	 Monocyte intracellular quantification of GSK3206944.
 [S4] To understand the extent of target engagement (TE) after ex vivo LPS challenge following single and repeat oral doses of GSK3358699 in healthy male participants. P1: Primary Objective 1 – Safety 	 Plasma concentrations of monocyte chemoattractant protein (MCP)-1, interleukin (IL)-6 and tumour necrosis factor (TNF) in blood stimulated ex vivo with LPS over time.

S1: Secondary Objective 1 – GSK3358699 systemic PK

S2: Secondary Objective 2 - GSK3206944 systemic PK

S3: Secondary Objective 3 - GSK3206944 intracellular PK

S4: Secondary Objective 4 - TE

2.3. Study Design

This study will be a randomised, double-blind (sponsor open), placebo-controlled, three part study of oral administration of GSK3358699 in healthy male participants. Part A will be a single ascending dose crossover design in two interlocking cohorts of participants (Cohorts 1 and 2). Part B will be a single dose, open-label two-way crossover study with GSK3358699 administered under fed and fasted conditions in a further cohort of participants (Cohort 3). Part C is planned to be a repeat dose design in 5 sequential cohorts of participants (Cohorts 4-8).

207546

All participants in Part A, Part B and Part C of the study will attend a screening visit within 35 days prior to their first dose (with the exception of Cohort 8 where the screening visit will be within 45 days prior to their first dose) and a follow up visit within 7-14 days of their last dose. A second follow up visit will also be conducted approximately 5 weeks after the last dose for those participants in cohorts where challenges and blisters are being administered. If warranted, additional follow-up visits may be scheduled.

Note: Due to early termination of the study Parts B and C were not completed as planned. No subjects were randomised or dosed in Part B and subjects were only dosed in Cohorts 4 and 5 of Part C.

Part A: Single Ascending Doses and LPS / GM-CSF challenges Treatment Period 1 **Treatment Period 2 Treatment Period 3** Treatment Period Cohort 1 (n=9) Cohort 1 – In Vivo 10 mg 35 mg 1 mg QD LPS Challenge + QD QD Blisters In Vivo Challenges Cohort 2 (n=9) Cohort 2 – In Vivo 45 mg 3 ma 20 mg GM-CSF Challenge QD QD QD + Blisters Evaluation of safety and tolerability plus PK and PD data review Part A Participants who are randomised into Part A can be enrolled in • Design another part of the study if they still fulfil all eligibility criteria features (which means that participants having received LPS challenge in Part A will not be eligible to participate in another part of the study). • In the Part A dose escalation phase (treatment periods 1-3), there will be two interlocking cohorts (Cohorts 1 and 2) each with up to 9 healthy participants. Each participant will receive a maximum of 2 single ascending oral doses of GSK3358699 and 1 placebo dose. At each dose level, GSK3358699 and placebo will be administered • in a 2:1 ratio, within each period, according to the randomisation schedule, in a blinded manner. Up to a maximum of 6 dose levels will be studied in total in Part A. Participants who are enrolled in the dose escalation treatment Periods of Part A may choose to only take part in the dose escalation treatment Periods 1-3, or may choose to also take part in the challenge treatment period (Period 4). If a participant chooses to participate in the dose escalation treatment Periods 1-3 only, or does not (at screening) meet the eligibility criteria specific to challenges (treatment Period 4), a new participant

The table below provides an overview of the study design and the key features.

e Ascending Doses and LPS / GM-CSF challenges
 will be recruited for treatment Period 4 only and will be regarded as a replacement participant. If a subject prematurely discontinues the study during Part A, additional replacement participants will be recruited and assigned to the same treatment sequence, starting from the next planned dosing Period following the premature discontinuation. Staggering of the first two participants (sentinel dosing) will be implemented in each cohort in each treatment period for this single dose phase. No participant will be a sentinel participant more than once. On Day 1, one of the two participants will receive the active dose and the other will receive placebo. Assuming adequate safety from these two participants over the first 48 hrs post-dose, the remaining participants in the cohort can then be dosed. Data, and hence dose level, will be reviewed between each period. There will be a minimum 14 days between the start of dosing (i.e. dosing of sentinel participants) in Cohort 1 and Cohort 2 in each treatment period. The decision to proceed to the next dose level of GSK3358699 will be made at a Dose Escalation Committee (DEC) meeting Upon conclusion of the dose escalation phase of Part A, an additional dosing period (treatment period 4) will be included. Participants in both cohorts will attend the clinic for outpatient visits, on Day -10 (± 3 days) to have control blister sample taken at a timepoint between approximately 48hrs post-blister induction. Participants in Cohort 1 will be administered an IV in vivo LPS challenge at a dose of 0.75 ng/kg following treatment with GSK3358699 or placebo and will then have blisters induced on the forearm (0.2% cantharidin) approximately 20 minutes after the challenge. The final selection of LPS dose will take into account all available pre-clinical and clinical safety and PD data at the time of study initiation. Participants in Cohort 2 will be administered 60 µg/m² in vivo GM-CSF challenge as an IV infusion followin
Refer to Appendix 1: Schedule of Activities

[figure not shown]
Part A: Sing	le Ascendi	ng Dose	es and L	PS / GN	-CSF challe	nges		
Part A	• Illust	ration o	f actual	treatme	nts after do	se escalation	on in Part	A.
Treatmen			Perio		Period		Period	1
t	Cohort	N=3	Р		10mg		40mg	
sequences	1	N=3	1mg		P		40mg	
-		N=3	1mg		10mg		P	
	Cohort	N=3	Ŭ	Р		20mg		30mg
	2	N=3		3mg	ξ	Р		30mg
		N=3		3mg	5	20mg		Р

	 In Cohort 5-8, participants will be randomised in a 1:1 ratio to receive either GSK3358699 or placebo, according to the randomisation schedule, once daily from Day 1 to Day 14 inclusive. On Day 14 of Cohorts 4 and 8, an IV in vivo LPS challenge at a dose of 0.75 ng/kg or a 60 µg/m² GM-CSF challenge as an IV infusion will be administered, followed by blister induction. LPS / GM-CSF administration may be performed at low systemic concentrations of GSK3358699 when intracellular concentrations of the acid GSK3206944 are high; The decision on the timepoint for administration will be based on emerging data and will be no more than 24 h after dosing with GSK3358699 or placebo on Day 14. In Cohort 4, of the 14 randomised participants, 7 will receive LPS challenge and 7 GM-CSF challenge. Of the 7 participants receiving each challenge, 5 will be randomised to receive GSK3358699 and 2 to receive placebo at the start of the cohort. In Cohort 8, of the 20 randomised participants, 10 will receive LPS challenge and 10 GM-CSF challenge. Of the 10 participants receiving each challenge, it is planned that 5 will be randomised to receive GSK3358699 and 5 to receive placebo. 		
Part C Time &	• Refer to Appendix 1: Schedule of Activities		
Events			
Part C Treatment Sequences	Within each cohort participants will be assigned to either GSK3358699 or placebo in a 5:2 ratio (Cohort 4) or a 1:1 ratio (Cohorts 5-8). The treatments will be determined following the completion of Part A. The treatment codes will be:		
	Treatment code Treatment Description		
	I 10 mg GSK3358699 RD		
	J 10 mg GSK3358699 RD		
	P Placebo		

2.4. Statistical Analyses

The primary objective is to determine the safety and tolerability of single and repeat oral doses of up to 14 days with GSK3358699 in healthy participants.

There are no formal hypotheses being tested in the study.

An estimation approach will be used to quantify the single dose PK for each dose level studied and also to assess PK parameters following 14 days repeat dosing relative to single dosing.

207546

3. PLANNED ANALYSES

3.1. Final Analyses

The final planned analyses (Parts A, B and C) will be performed after the completion of the following sequential steps:

- 1. All participants have completed the study as defined in the protocol (Section 5.3 of the protocol): The end of the study is defined as the date of the last visit (including follow-up) of the last participant in the study (Parts A, B and Part C).
- 2. All required database cleaning activities have been completed and final database release (DBR) and database freeze (DBF) has been declared by Data Management.
- 3. All criteria for unblinding the randomisation codes have been met.
- 4. Randomisation codes have been distributed according to RandAll NG procedures.

Due to the early termination of the study, the planned exploratory analysis will not be included in the main SAC delivery. Exploratory analysis will be performed separately in cases where it is deemed clinically or scientifically relevant. The study was terminated prior to any subjects being dosed with study treatment in Part B and therefore only minimal listings of screening data will be produced for this part.

207546

4. ANALYSIS POPULATIONS

Population	Description	Outputs
Enrolled	• All participants who sign the ICF	• Study Population (specific only)
Screened	• All participants who were screened for eligibility	• Study Population (specific only)
Safety	 All screened participants who received at least one dose of study treatment. This population will be based on the actual treatment the participant received. 	 Study Population (all others) Safety PD
РК	 All participants in the Safety population who receive an active dose and for whom a PK sample was obtained and analysed. This population will be based on the actual treatment the participant received. 	• PK
	Note: Non-quantifiable [NQ] values will be considered as non-missing values for the purposes of deriving the PK population.	

4.1. Protocol Deviations

Important protocol deviations (including deviations related to study inclusion/exclusion criteria, conduct of the trial, patient management or patient assessment) will be summarised and listed.

Protocol deviations will be tracked by the study team throughout the conduct of the study in accordance with the Protocol Deviation Management Plan.

- Data will be reviewed prior to unblinding and freezing the database to ensure all important deviations are captured and categorised on the protocol deviations dataset.
- This dataset will be the basis for the listings of protocol deviations.

A separate listing of all inclusion/exclusion criteria deviations will also be provided. This output will be based on data as recorded on the inclusion/exclusion page of the eCRF.

5. CONSIDERATIONS FOR DATA ANALYSES AND DATA HANDLING CONVENTIONS

5.1. General

Separate outputs will be generated for each of Parts A, B and C. The presence of participants taking part in multiple parts/cohorts of the study will be appropriately notified in the relevant Safety outputs.

5.2. Study Treatment Display Descriptors

In the Tables, Listings and Figures (TLF), treatment should be presented with placebo first, then in order of increasing dose within each part.

Part A	Part A: Treatment group descriptions				
Rand	andAll NG Data displays for reporting				
Code	RandAll description	Table/FigureListing LabelOrder in T		Order in TLF	
		Label			
А	1 mg GSK3358699 SD	1 mg SD	1 mg SD – A	2	
В	3 mg GSK3358699 SD	3 mg SD	3 mg SD – B	3	
С	10 mg GSK3358699 SD	10 mg SD	10 mg SD – C	4	
D	20 mg GSK3358699 SD	20 mg SD	20 mg SD – D	5	
Е	35 mg GSK3358699 SD	40 mg SD	40 mg SD – E	8	
F	45 mg GSK3358699 SD	30 mg SD	30 mg SD – F	7	
R	Dose X GSK3358699 SD	25 mg SD	25 mg SD – R	6	
P Placebo SD		Placebo SD	Placebo SD – P	1	
Note: doses in RandAll descriptions and display descriptions differ for treatments E, F, R					
due to DEC decisions.					

Part C: Treatment group descriptions					
RandAll NG		Data displays for reporting			
Code	Description	Table/Figure Label	Listing Label	Order in TLF	
Ι	Dose 1 GSK3358699 RD	10 mg RD	10 mg RD - I	2	
J	Dose 2 GSK3358699 RD	10 mg RD	10 mg RD - I	2	
QPlacebo RDPlacebo RD - Q			1		
Note: the same dose level was administered in both Cohorts 4 and 5 due to the early					

Note: the same dose level was administered in both Cohorts 4 and 5 due to the early termination of Cohort 4. Subjects in the active treatment group from both cohorts will be summarised and listed under the same treatment label.

207546

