11 DECEMBER 2018

Date

[name], PhD Interim Head of Discovery Medicine Clinical Pharmacology and Experimental Medicine Research R&D

PROTOCOL AMENDMENT SUMMARY OF CHANGES TABLE

DOCUMENT HISTORY		
Document	Date	
Amendment 4	11-DEC-2018	
Amendment 3	29-MAY-2018	
Amendment 2	21-MAR-2018	
Amendment 1	25-JAN-2018	
Original Protocol	30-NOV-2017	

Amendment 4: 11-DEC-2018

Overall Rationale for the Amendment:

Four asymptomatic, non-serious, non-severe and self-limiting cardiac arrhythmias were observed in the study. A temporary dosing hold was implemented during Cohort 4 (Part C) to allow sufficient time for safety panel review of these events. As described in this protocol amendment, Part C of the study will commence from Cohort 5 with an additional cohort added to provide four full planned cohorts (Cohorts 5-8).

Additionally, the randomization ratio has been changed to 1:1 (Active:Placebo) in Part C, to provide a balanced comparison between subjects on active and placebo. Furthermore, the Part C study design has been modified to remove the *in vivo* challenges from Cohorts 5, 6 and 7 to limit unnecessary exposure of participants receiving placebo to immunological challenge, and to attenuate study duration and complexity.

Exclusion criteria have been revised to exclude individuals who may be at higher natural risk of cardiac arrhythmias.

An interim analysis following Cohort 7 has also been included to allow formal readout of data obtained up to that point whilst Cohort 8 (which are primarily experimental endpoints) is still ongoing.

In addition, further administrative clarifications have been made.

The specific revisions are summarised below:

Section # and Name	Description of Change	Brief Rationale
Sponsor Signatory	Change of Sponsor Signatory to	Sponsor Signatory has changed.
page	[name].	
Synopsis and Section	Added 'is planned to' to final sentence	Increased flexible wording; change in
5.1; Overall Design	regarding Part C and amended number of cohorts.	study design.
Synopsis; Number of participants	Table updated to reflect new cohorts and number of participants required for each.	Change in study design / randomisation requirements.
	Text added to state that Part C participants may take part in a later Part C cohort if they fulfil all eligibility criteria.	Increased flexibility.

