5.2. Number of Participants

The number of healthy male participants and the required number of evaluable participants are outlined in Table 1.

Part	Participants per cohort	Evaluable participant number per cohort	Evaluable participant definition
A (Cohorts 1-2)	9 (6:3 GSK3358699 : Placebo)	6	Complete both screening and all their planned treatment Periods.
B (Cohort 3)	6 (all receive GSK3358699)	5	Complete both screening and both treatment Periods.
C (Cohort 4)	14 (10:4 GSK3358699 : Placebo)	9	Complete both screening and the 14 day treatment Period and subsequent 48 h assessment Period.
C (Cohorts 5-7)	18 (9:9 GSK3358699 : Placebo)	12	Complete both screening and the 14 day treatment Period and subsequent 48 h assessment Period
C (Cohort 8)	20 (10:10 GSK3358699 : Placebo)	14	Complete both screening and the 14 day treatment Period and subsequent 48 h assessment Period.

Table 1 Number of Participants

2017N332348_05

CONFIDENTIAL

Participants who are randomized into a particular part of the study can be enrolled in another part of the study, as well as be enrolled in a later cohort of the same part of the study in Part C, if they still fulfil all eligibility criteria (which means that participants having received LPS challenge in Part A will not be eligible to participate in another part of the study).

Additional participants/cohorts may be enrolled in Part A or Part C to allow for evaluation of additional dose levels or alternative regimens, including for challenges, as detailed in Section 7.2. No more than 9 additional participants will be included as part of a new cohort in Part A and no more than 20 additional participants will be allowed as part of a new cohort in Part C (ie in addition to Cohort 4-8 participants).

If participants prematurely discontinue the study during Part A, additional replacement participants may be recruited and assigned to the same treatment sequence, starting from the next planned dosing Period following the premature discontinuation, at the discretion of the Sponsor in consultation with the investigator.

If a participant chooses to participate in, or is eligible for, the dose escalation treatment Periods only in Part A as described in Section 5.1.1.1, a new participant will be recruited for the challenge treatment period (treatment Period 4) only and will be regarded as a replacement subject, assigned to the same treatment sequence. This will occur at the discretion of the Sponsor in consultation with the investigator.

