5.4. Re-enrolled Participants

The protocol allows participants to take part in more than one cohort in this study. Instances where this occurred were as follows:

Subject Number				
Cohort 1	Cohort 2	Cohort 2 Cohort 4 Cohort 5		
PPD		PPD		
	PPD		PPD	
		PPD	PPD	

207546

Participants who take part in more than one cohort are to be considered distinct participants for the purposes of the reporting of all the data in this study. However relevant displays will be footnoted.

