13.9.6. Safety Figures

Part A

Safety	Safety: Figures						
No.	Population	IDSL / Example Shell	Title	Programming Notes	Deliverable [Priority]		
Adver	se Events						
2.1.	Safety	AE10	Part A: Plot of Common (>=5%) Adverse Events and Relative Risk		SAC		

Part C

Safety	Safety: Figures							
No.	Population	IDSL / Example Shell	Title	Programming Notes	Deliverable [Priority]			
Adver	se Events							
2.2.	Safety	AE10	Part C: Plot of Common (>=5%) Adverse Events and Relative Risk		SAC			

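### Pooling Part C Cohorts 4 and 5 across different randomisation ratios and cardiac exclusions may bias the crude relative risks in Figure 2.2, in either direction

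*SAP*

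**What the plan says.** The Part C table in SAP 5.2 lists two active codes, I and J. Both appear as 10 mg RD in tables and figures and as 10 mg RD - I in listings. There is one placebo row. The note below gives the reason (the same dose was used in both cohorts after Cohort 4 ended early) and concludes: "Subjects in the active treatment group from both cohorts will be summarised and listed under the same treatment label". That sentence covers the active arms only; the pooling of placebo is read from the table.

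On allocation, SAP 2.3 assigns participants to active or "placebo in a 5:2 ratio (Cohort 4) or a 1:1 ratio (Cohorts 5-8", as does Protocol 7.3. Table 1 in Protocol 5.2 plans Cohort 4 as "14 (10:4 GSK3358699 : Placebo" and each of Cohorts 5 to 7 as "18 (9:9 GSK3358699 : Placebo". SAP 2.3 reports that "subjects were only dosed in Cohorts 4 and 5 of Part C", so the pool mixes exactly these two ratios.

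Cohort 4 stopped on 14 November 2018 (SAP 13.6.1). Protocol Amendment 4, dated 11 December 2018, then changed the ratio, removed the challenges from Cohorts 5 to 7 and altered eligibility: "Exclusion criteria have been revised to exclude individuals who may be at higher natural risk of cardiac arrhythmias". One new criterion excludes anyone with non-sustained ventricular tachycardia (NSVT) or frequent ventricular premature beats on the screening Holter (Protocol 6.2, exclusion 8).

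Figure 2.2 in SAP 13.9.6 is titled "Part C: Plot of Common (>=5%) Adverse Events and Relative Risk". Neither it nor the Part C safety tables in SAP 13.9.5 carry a cohort stratum, a by-cohort column or a sensitivity analysis. Under SAP 5.4, "Participants who take part in more than one cohort are to be considered distinct participants", with footnotes; one person was in both Cohorts 4 and 5.

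**The concern.** Within each cohort, randomisation protects the comparison of active with placebo. Once two cohorts with different ratios are added together without stratification, the active and placebo groups have a different cohort mix. A difference in background risk between the cohorts then shows up as an apparent treatment difference.

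Arrhythmia is the event for which this matters most. Protocol 3.3.1 records two NSVT cases in Part C by the time of Amendment 4, when Cohort 4 was the only Part C cohort that had started. The new exclusions were meant to lower the natural risk in later cohorts. The same section lists the 1:1 ratio among the NSVT mitigations, and the amendment rationale says it was adopted for balance between active and placebo. If both cases were recorded as adverse events in separate participants, they would be 2/32 = 6.3% of the planned pool, above the 5% threshold of Figure 2.2 if that threshold is applied to Part C as a whole. Safety is the primary objective, and a relative-risk plot will be read as a statement about the drug.

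**Working it through.** **Inputs.** Planned sizes are from Protocol 5.2. The cohort event risks p4 and p5 are not in the documents, so their ratio r = p4/p5 is an assumption and is varied.

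**1. The plan's own figures.** 10 + 4 = 14, which reduces to 5:2. 9 + 9 = 18, which reduces to 1:1. Both reproduce.

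**2. Cohort mix after pooling.** Active: 10 + 9 = 19, of whom Cohort 4 supplies 10/19 = 52.6%. Placebo: 4 + 9 = 13, of whom Cohort 4 supplies 4/13 = 30.8%.

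**3. Crude relative risk with no drug effect** (ratio of expected risks):

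RR = [(10·p4 + 9·p5)/19] ÷ [(4·p4 + 9·p5)/13]

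For r = 2 this is (29/19) ÷ (17/13) = 1.526/1.308 = 1.17. For r = 5 it is (59/19) ÷ (29/13) = 3.105/2.231 = 1.39.

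| r = p4/p5 | Crude RR, no drug effect |
|---|---|
| events only in Cohort 5 | (9/19)/(9/13) = 0.68 |
| 0.2 | 0.77 |
| 0.5 | 0.87 |
| 1 | 1.00 |
| 2 | 1.17 |
| 3 | 1.27 |
| 5 | 1.39 |
| events only in Cohort 4 | (10/19)/(4/13) = 1.71 |

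**4. The same data stratified by cohort.** With no drug effect, the Mantel-Haenszel numerator and denominator are identical: (10·4/14)·p4 + (9·9/18)·p5. The ratio is 1.00 for every r, and the corresponding risk difference is 0.

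**5. Sensitivity to realised sizes.** These are not given. For assumed enrolments of 10:4 or 5:2 in Cohort 4 with 4:4 to 9:9 in Cohort 5, r = 2 gives 1.14 to 1.17. The limit with all events in Cohort 4 lies between 1.43 and 1.96, and the limit with all events in Cohort 5 between 0.57 and 0.79.

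**6. Comparison with random error.** Take assumed risks of 0.4 in Cohort 4 and 0.2 in Cohort 5. Expected events are 10(0.4) + 9(0.2) = 5.8 of 19 on active and 4(0.4) + 9(0.2) = 3.4 of 13 on placebo, so RR = 1.17. The standard error of log RR is √(1/5.8 − 1/19 + 1/3.4 − 1/13) = 0.58, giving an approximate 95% CI of 0.37 to 3.64.

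**The case against.** A reader might infer that the Part C relative risks are confounded as a matter of fact, and inflated against the drug. The documents do not support that. They give no event rates by cohort, and at equal risk the bias is zero. The direction is also open:

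- Cardiac disease was already excluded before Amendment 4, so the change tightened existing rules. Nothing shows that it altered the risk of adverse events in general.
- The amendment history in Protocol Appendix 8 puts the upper age limit for challenge participants at 55, whereas Protocol 6.1 allows up to 65 in Cohorts 5 to 7. This could raise risk in Cohort 5.
- Both cohorts stopped with some participants part way through treatment, and later safety data are left out of summaries (SAP 13.6.1). Follow-up per cohort is unknown.
- The Cohort 4 challenges were due on Day 14, and the number challenged is not stated. The Day -10 blisters precede routine adverse event collection, which begins with treatment (Protocol 9.2.1).

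A reader might also infer that pooling cancels the benefit of the 1:1 ratio. That too goes further than the documents. Cohort 5 keeps its internal balance, subject numbers fall in cohort-specific ranges (Protocol 6.4), and adverse events and abnormal ECG findings are listed by participant (Listings 45, 46 and 59 to 62). A rare arrhythmia can therefore be traced to its cohort and arm.

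Other points are fair. The study tests no hypotheses, the same dose is a reasonable ground for combining active exposure, and random error exceeds the bias. A stratified ratio is fragile: with four planned placebo participants in Cohort 4, an event with 20% risk is absent from that cell with probability 0.8⁴ = 41%. Output shells are kept outside the SAP and were not available. The repeat participant is disclosed in SAP 5.1, SAP 5.4 and the note to Table 1.12.

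These points limit the size and certainty of the problem. They do not correct a crude ratio: listings leave the plot unchanged, and imprecision is no reason to keep a systematic error that stratification removes.

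**Conclusion.** The point holds as a conditional one. Pooling ties treatment to cohort, and the unstratified relative risks in Figure 2.2 may be biased in either direction for any event whose background risk differs between Cohorts 4 and 5. At planned sizes with no drug effect, a two-fold higher risk in Cohort 4 gives 1.17 and a two-fold lower risk gives 0.87; no cohort difference can take the ratio outside 0.68 to 1.71. These figures assume the planned 10:4 and 9:9 and chosen risk ratios; realised sizes and cohort risks are not in the documents. The effect is confined to descriptive displays and is smaller than their random error. It is still worth correcting, because it bears on the primary safety objective and most plausibly on arrhythmia. Counting one participant twice in the pooled denominators is a minor, disclosed matter.

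**What to change.** - Show the Part C adverse event and ECG summaries by cohort within treatment, with a total column. The pooled totals can stay.
- Base Figure 2.2 on a cohort-stratified estimate with a 95% CI. A Mantel-Haenszel risk difference tolerates zero cells; a stratified relative risk can be added where it is estimable. Label any crude figure as crude.
- Repeat the pooled results without the second enrolment of the participant who was in both cohorts, and report whether anything changes.

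The cost is some SAP wording, one stratification variable in the programs, somewhat wider tables and one short sensitivity run. No new data are needed.
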